1 STATEMENT OF COMPLIANCE

The study trial will be carried out in accordance with Good Clinical Practice (GCP) and as required by the following:

- United States Code of Federal Regulations (CFR) 45 CFR Part 46: Protection of Human Subjects
- Food and Drug Administration (FDA) Regulations, as applicable: 21 CFR Part 50 (Protection of Human Subjects), 21 CFR Part 54 (Financial Disclosure by Clinical Investigators), 21 CFR Part 56 (Institutional Review Boards), 21 CFR Part 11, and 21 CFR Part 312 (Investigational New Drug Application), 21 CFR 812 (Investigational Device Exemptions)
- International Conference on Harmonisation: Good Clinical Practice (ICH E6); 62 Federal Register 25691 (1997); and future revisions
- Belmont Report: Ethical Principles and Guidelines for the Protection of Human Subjects of Research, Report of the National Commission for the Protection of Human Subjects of Biomedical and Behavioral Research
- National Institutes of Health (NIH) Office of Extramural Research, Research Involving Human Subjects, as applicable
- National Institute of Allergy and Infectious Diseases (NIAID) Clinical Terms of Award, as applicable
- Applicable Federal, State, and Local Regulations and Guidance

6 LIST OF ABBREVIATIONS

| | |
|---------|--|
| AE | Adverse Event/Adverse Experience |
| BLA | Biologics License Applications |
| CAR | Clinical Agents Repository |
| CFR | Code of Federal Regulations |
| CI | Confidence Interval |
| CIOMS | Council for International Organizations of Medical Sciences |
| CONSORT | Consolidated Standards of Reporting Trials |
| CRF | Case Report Form |
| CRO | Contract Research Organization |
| CSR | Clinical Study Report |
| DCC | Data Coordinating Center |
| DHHS | Department of Health and Human Services |
| DMID | Division of Microbiology and Infectious Diseases, NIAID, NIH, DHHs |
| DSMB | Data and Safety Monitoring Board |
| eCRF | Electronic Case Report Form |
| EED | Environmental Enteric Dysfunction |
| FDA | Food and Drug Administration |
| FDAAA | Food and Drug Administration Amendments Act |
| FWA | Federal Wide Assurance |

| | |
|---------|---|
| GCP | Good Clinical Practice |
| HIPAA | Health Insurance Portability and Accountability Act |
| HIV | Human Immunodeficiency Virus |
| IB | Investigator's Brochure |
| ICF | Informed Consent Form |
| ICH | International Conference on Harmonisation |
| ICMJE | International Committee of Medical Journal Editors |
| IDE | Investigational Device Exemption |
| IEC | Independent or Institutional Ethics Committee |
| IND | Investigational New Drug Application |
| IRB | Institutional Review Board |
| ISM | Independent Safety Monitor |
| JAMA | Journal of the American Medical Association |
| MedDRA® | Medical Dictionary for Regulatory Activities |
| MOP | Manual of Procedures |
| N | Number (typically refers to subjects) |
| NDA | New Drug Application |
| NEJM | New England Journal of Medicine |
| NIAID | National Institute of Allergy and Infectious Diseases, NIH, DHHS |
| NIH | National Institutes of Health |
| OHRP | Office for Human Research Protections |

| | |
|--------------------|--|
| OHSR | Office for Human Subjects Research |
| PHI | Protected Health Information |
| PI | Principal Investigator |
| PD | Pharmacodynamics |
| PK | Pharmacokinetics |
| PSAC | Preschool aged children |
| PZQ | Praziquantel |
| iaQA | Quality Assurance |
| QC | Quality Control |
| SAE | Serious Adverse Event/Serious Adverse Experience |
| S. | Schistosoma genus |
| S.mansoni | Schistosoma mansoni |
| S.japonicum | Schistosoma japonicum |
| SMC | Safety Monitoring Committee |
| SOP | Standard Operating Procedure |
| UK | United Kingdom |
| US | United States |
| UVRI | Uganda Virus Research Institute |
| WHO | World Health Organization |

Protocol Summary

| | |
|---------------------------------------|--|
| Title: | Praziquantel for children under four: A Phase II PK/PD driven dose finding trial |
| Phase: | 2 |
| Population: | 
Sample size N=600
 
Sex: Male:Female (1:1)
 
Ages: 12 – 47 months old inclusive
 |
| Number of Sites: | Two: Uganda (N=300) and Philippines (N=300) |
| Study Duration: | 36 months |
| Duration of Subject participation | 13 months |
| Description of Agent or Intervention: | 
Baseline: Children will receive either
 
1-Praziquantel 40 mg/kg given as a single dose and placebo 3 hours later
 
or
 
2-Praziquantel 80 mg/kg (40 mg/kg followed by 40 mg/kg 3 hours later)
 
Six months post baseline: Praziquantel given at the child's baseline dose or placebo
 
Oral route – crushed tablets
 
12 months post baseline: Praziquantel only to children positive by any diagnostic test at same baseline dose.
 |
| Objectives: | 
Primary:
 
 To assess parasitologic cure and egg reduction rate of praziquantel (PZQ) at two different doses (40 mg/kg or 80 mg/kg split as two doses over three hours) among children aged 12-47 months. |

[figure not shown]
| | |
|-------------------|--|
| | 
Secondary:
 
 1. To assess the safety and efficacy and PK/PD of PZQ administered at different dose regimens. 2. To evaluate the PK/PD of both PZQ enantiomers given the concern that this has varied in studies of S. mansoni. 3. To expand PD endpoints for drug efficacy to include state-of-the art antigen tests to accurately capture residual worm burden (Circulating Cathodic and Anodic Antigens (CCA and CAA)). 4. To assess the safety and impact of PZQ treatment (dose and interval) on key measures of morbidity 6 and 12 months after initial treatment and mechanisms mediating morbidity 5. To further evaluate the safety of higher PZQ dosing (80 mg/kg) including bone marrow, renal, and liver toxicity as captured before dosing and 12 hours after. 6. To evaluate the mechanisms mediating the effect of varying treatment doses and frequencies on growth and nutritional morbidity 7. To evaluate the mechanistic role of Environmental Enteric Dysfunction (EED) in the pathogenesis of schistosomiasis related morbidities. 8. To explore immune responses to S. mansoni infection and treatment 9. To determine the prevalence and the pattern of schistosomiasis-related morbidity as determined by ultrasound scan. |
| Outcome Measures: | 
Primary:
 
Drug efficacy as per standard parasitological endpoints (Cure Rate and Egg Reduction Rate) at +/- 1 weeks post-PZQ
 
Secondary:
 |

| | |
|--|---|
| Description of Study Design: | 
 1. Drug efficacy assessed by novel antigenic endpoints (CCA and CAA) among all children, and in relation to PK/PD parameters associated with cure (Area-Under-the Curve (AUC)) at 4 +/- 1 weeks post-PZQ in a subset of children. 2. 12 hour clinical monitoring for safety including active capture of adverse events and assessment of toxicity through serum chemistries and hematologic parameters. 3. Iron status, hemoglobin, and age and gender adjusted longitudinal growth and nutritional status 4. Biomarkers of inflammation and EE including fecal calprotectin, urine lactulose:mannitol ratio, serum endotoxin, serum endotoxin core antibody, and proinflammatory cytokines 5. Inter-individual variability in PZQ AUC as modified by Environmental Enteric Dysfunction (EED) 6. Immune responses to S. mansoni infection and treatment 7. Prevalence and the pattern of schistosomiasis-related morbidity as determined by ultrasound scan. 
Four parallel arm randomized quasi-double blinded placebo-controlled trial with a 4 week, 6 months and 12 month follow up. Interventions will be given at baseline and at 6 months. Parasitological endpoints will be measured at 4 weeks. Morbidity endpoints will be measured at 6 and 12 months.
 |
| Estimated Time to Complete Enrolment: | 24 months |

Table 1: Treatment Arms*

| | Number of subjects | Baseline Dose | 6 months post baseline dose |
|-------|--------------------|---|---|
| ARM 1 | 150 | 40 mg/kg dose PZQ (40 mg/kg followed by Placebo 3 hours later) | Placebo followed by Placebo 3 hours later |
| ARM 2 | 150 | 40 mg/kg dose PZQ (40 mg/kg followed by Placebo 3 hours later) | 40 mg/kg dose (40 mg/kg followed by Placebo 3 hours later) |
| ARM 3 | 150 | 80 mg/kg split dose PZQ (40 mg/kg followed by 40 mg/kg 3 hours later) | Placebo followed by Placebo 3 hours later |
| ARM 4 | 150 | 80 mg/kg split dose PZQ (40 mg/kg followed by 40 mg/kg 3 hours later) | 80 mg/kg split dose (40 mg/kg followed by 40 mg/kg 3 hours later) |

*** These numbers represent subject totals across both sites. At each site, approximately N=75 subjects will be enrolled in each of the 4 arms providing N=300 subjects at each site.**

Figure 1: Schematic of Study design

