2.3.2. Known Potential Benefits

- 2.3.2.1. **Pediatric Care.** Children are likely to receive better pediatric care as many do not ever have a history and physical examination by a healthcare provider. Children will be examined by the study physician and be referred for care provided by the study as needed including iron and nutritional interventions. The same procedures will be followed for children at baseline and follow up.
- 2.3.2.2. **Parasitological results and treatment.** For all screened children, parents will be provided with results of stool screening for both schistosomiasis and soil transmitted

helminths, which is not part of standard care in the study area. For all schistosomiasis infected children recruited into the main study, we will provide praziquantel (40 or 80 mg/kg at baseline and 12 months after treatment if re-infected) with half of the children receiving a second dose at six months. In addition, albendazole treatment will be provided at baseline for children infected with soil-transmitted helminths and again at 12 months post-treatment if they are re-infected.

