3. *Study Visit 3 (6 months post enrolment)* Six months (+/- 2 weeks) following visit one, subjects will return to the respective field laboratories. They will receive either the same dose of Praziquantel as received at Visit 1 or placebo as determined at baseline randomization. At this

visit, and before the study drug or placebo is received, blood will be drawn for follow up assessment of morbidity, and in depth measures of nutritional status. An ultrasound scan will be performed. Blood (7 ml) will be collected for the same subset of N=150 subjects for studies of immunological responses. Urine will be stored at this visit for future processing of CAA to monitor re-infection.

4. Study Visit 4, Close out. (12 months post enrollment) Twelve months (+/- 2 weeks) post enrollment and initial treatment, study subjects will return to the field laboratory. Prior to this visit they will be asked to provide three stool samples and one urine. At this visit, blood will be drawn for follow up morbidity studies and in-depth measures of nutritional status will be made. All children will be treated with Praziquantel and those infected with soil-transmitted helminths will be treated with albendazole 200 mg (12 – 24 month old children) or albendazole 400 mg (children over age two). A repeat ultrasound scan will be done before the participant is discharged from the study. If however, the ultrasound scan at six months revealed resolution of any pathology detected at baseline, there will be no repeat at discharge. Blood (7 ml) will be collected for the same subset of N=150 subjects for studies of immunological responses.

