7.6. Follow-up and close out at 12 months

The following activities will take place at the respective research laboratories. This visit will take approximately 5-6 hours with no overnight admission. Technical work in this phase will be performed by Ministry of Health personnel (Vector Control Division).

- Weight, height, clinical history
- Lactulose/Mannitol beverage. They will take 2ml/kg of lactulose-mannitol solution (containing 250 mg/mL lactulose and 50 mg/mL mannitol in purified water, in aliquots of 20ml) up to a maximum of 20 ml. Urine will be collected for 2 hours after ingestion of the solution. 2ml aliquots of each of the urine samples will be collected and stored between 2 – 8°C for lactulose-mannitol assay.
- **Urine** test for CAA/CCA assay
- **Stool** collection for:
 - Calprotectin and fecal occult blood (performed on site).
 - Kato Katz (two samples in Uganda and three in Philippines) with some collected prior to visit
- **Urine** collection for CCA and CAA
- **Blood:** Five ml for morbidity studies including CBC, iron biomarkers, EED biomarkers, pro-inflammatory cytokines and further 7 ml from the sub-group of N=150 children who were selected at baseline for immunology assays (such as flow cytometry, Luminex, ELISpot and ELISA).
- **PZQ** administration at the study assigned dose after a meal consisting of local foods for children infected with schistosomiasis based on Kato-Katz or urine CCA
- **Albendazole** administration for any child infected with soil-transmitted helminths

- **Ultrasound** to determine persistence of morbidity

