7.7. Final Study Visit

This visit will occur with the 12 month follow up visit as above. Technical work in this phase will be performed by Ministry of Health personnel (Vector Control Division). All children will be treated for schistosomiasis as per Uganda DOH and WHO recommendations.

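### The protocol gives conflicting rules on who receives praziquantel at 12-month close-out and, for arms 3 and 4, at what dose; the masked supply and post-dose observation for that dose are not worked out

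*Combined protocol and SAP*

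**What the plan says.** Five places state who is treated at 12 months.

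- Protocol Summary, Description of Agent or Intervention: "12 months post baseline: Praziquantel only to children positive by any diagnostic test at same baseline dose".
- Section 2.3.2.2: "we will provide praziquantel (40 or 80 mg/kg at baseline and 12 months after treatment if re-infected".
- Section 4.2, Study Visit 4: "All children will be treated with Praziquantel and those infected with soil-transmitted helminths will be treated" with albendazole. No praziquantel dose is given.
- Section 7.6 lists praziquantel "administration at the study assigned dose after a meal consisting of local foods for children infected with schistosomiasis based on Kato-Katz or urine CCA".
- Section 7.7: "All children will be treated for schistosomiasis as per Uganda DOH and WHO recommendations". It is not a separate occasion: "This visit will occur with the 12 month follow up visit as above".

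On supply, Table I in section 4.2 defines vial letters A to D, two for baseline and two for 6 months. Sections 5.3.2 and 6.2 describe dosing at those two visits, and the Protocol Summary's design description places the interventions there.

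On observation, section 9.1 requires 12 hours of adverse-event monitoring after each administration of investigational product during the trial. Section 7.6 says of the 12-month visit: "This visit will take approximately 5-6 hours with no overnight admission". Section 7.5 lists adverse-event monitoring after the 6-month dose; section 7.6 lists none after the 12-month dose. Section 9.4 gives discharge times for enrolment and 6 months only.

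**The concern.** The section a site follows decides whether a test-negative child, aged 24 to 59 months by then (12 + 12 to 47 + 12), receives praziquantel at all. In arms 3 and 4 it also decides whether the child receives 80 or 40 mg/kg. Section 2.3.1 names exposure to more than the routine dose as the main risk of the trial, so repeat dosing at 80 mg/kg should not turn on which page staff read.

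Two practical gaps follow if the assigned dose is meant. No masked 12-month supply is described, so giving it could show site staff which dose group a child is in. The visit length also does not fit the general monitoring rule, if that rule covers this dose.

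**Working it through.** There is no planned figure to reproduce. The check sets the sections against each type of child, then compares visit times.

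**1. Who is treated, and at what dose.** Section 7.7 gives no figure; the 40 mg/kg entries take the WHO dose from section 2.2 and assume the Ugandan recommendation does not differ.

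| Child at 12 months | Protocol Summary, 2.3.2.2, 7.6 | 4.2, Study Visit 4 | 7.7 read with 2.2 |
|---|---|---|---|
| Test-negative, any arm | No dose | Treated, dose not stated | 40 mg/kg |
| Positive, arms 1 and 2 | 40 mg/kg | Treated, dose not stated | 40 mg/kg |
| Positive, arms 3 and 4 | 80 mg/kg | Treated, dose not stated | 40 mg/kg |

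Only the middle row is consistent. Study Visit 4 cannot be rescued by reading all as all infected, because the same sentence contrasts all children, who get praziquantel, with the helminth-infected, who get albendazole.

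**2. How many children.** Section 11.2 allows 10% attrition: 600 × 0.90 = 540 at 12 months. Arms 3 and 4: 300 × 0.90 = 270, assuming equal attrition by arm. The conflict on eligibility touches every test-negative child among the 540; the conflict on dose touches the positive children among the 270. Without a 12-month positivity figure, neither count can be given.

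**3. Supply.** Under the assigned dose, arms 1 and 2 need active drug then placebo, and arms 3 and 4 need active drug twice. Table I has no vial for either dose at 12 months. Section 5.3.1 speaks of two vials for each study visit, but read with Table I that means baseline and 6 months.

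**4. Observation.** Section 9.1 requires 12 h.

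- 12 months, single dose given on arrival (most favourable case): 12 − 6 = 6 h to 12 − 5 = 7 h short.
- 12 months, dosing after the lactulose-mannitol test as at baseline (assumption): the 2 h urine collection, plus up to 0.5 h fasting and up to 0.5 h after the meal, puts the first dose at 2 to 3 h. A 5 to 6 h visit leaves between 5 − 3 = 2 h and 6 − 2 = 4 h, so it is 8 to 10 h short.
- Same order with a split dose: the second dose falls at 5 to 6 h. The visit ends at most 1 h after it, and in the tightest case 1 h before it.
- 6 months: section 9.4 implies discharge 3 to 4 h after dosing, so 12 − 4 = 8 h to 12 − 3 = 9 h short. The mismatch is not peculiar to close-out.

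**The case against.** The strongest reply is that this is clinical care at the end of the trial. The dose comes 11 months after the primary endpoint, and no outcome listed in section 11.1 uses it. The word only appears in the Protocol Summary alone; sections 2.3.2.2 and 7.6 say infected children are treated without expressly barring others. Three sections agree on the assigned dose, and Study Visit 4 is silent on dose rather than contrary. Supply details may sit in the manual of procedures. All of this limits the consequences, but the Protocol Summary still excludes test-negative children whom two other sections treat, and a manual that picks one rule leaves sites departing from another section.

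A reader might infer more than the documents support:

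- *That no observation period exists for this dose.* Section 9.1 sets one. The supportable point is the misfit with the visit length, and only if the close-out dose counts as investigational product. The Protocol Summary's placing of interventions at baseline and 6 months leaves that open.
- *That a child positive only by CAA is treated under one section and not another.* Section 7.6 does list a urine "test for CAA/CCA assay", but nothing says a CAA result is available when the dosing decision is made, and the 6-month urine is stored for later CAA processing.
- *That the blind or the results are seriously compromised.* Section 2.1 already accepts that staff may tell the tablets apart. Site staff inferring a dose does not by itself breach section 15.4, which concerns analysis before the code is broken. The residual exposure is mainly the exploratory ultrasound outcome, since the protocol does not say the close-out scan precedes dosing.

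**Conclusion.** The protocol is wrong as written on close-out treatment. It conflicts on eligibility for every test-negative child among about 540 attending. It also conflicts on dose (80 against 40 mg/kg) for positive children among about 270 in arms 3 and 4. These figures rest on the planned 10% attrition, equal attrition by arm, and section 2.2's statement of the WHO dose.

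The missing masked supply is a small, avoidable risk to the blind. The observation mismatch is conditional on the status of the close-out dose, and applies at 6 months as well. The 4-week primary outcome precedes this dose, and the 12-month anthropometric and haemoglobin outcomes are essentially unaffected. The point deserves correction for safety and consistent conduct, not because it threatens the main comparisons.

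**What to change.** Amend the Protocol Summary and sections 2.3.2.2, 4.2 (Study Visit 4), 7.6 and 7.7 to one rule, chosen by the sponsor's clinicians. Either conform Study Visit 4 and section 7.7 to section 7.6 (children positive by Kato-Katz or urine CCA), or treat all children throughout. State one dose basis, valid for both countries, with dosing after all 12-month assessments. There are two routes:

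1. **Open-label close-out treatment.** For example: *After all 12-month assessments, [all children / children positive by Kato-Katz or urine CCA] receive open-label praziquantel at [one stated dose, the same in all arms, such as 40 mg/kg]. This treatment is outside the randomised comparison. Children are observed for [stated] hours.* A common dose does not reveal the arm.
2. **Assigned dose kept.** Add a masked 12-month vial pair to Table I and cover the visit in sections 5.3.2 and 6.2.

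Under either route, list post-dose monitoring in section 7.6, say whether the close-out dose is investigational product, and reconcile section 9.1 with both the 6-month and 12-month visits.

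The cost is a protocol amendment with IRB/IEC approval (section 14.2), plus a small unmasked stock for route 1 or one more vial pair per child for route 2. Bringing the visits up to 12 hours would lengthen them; otherwise section 9.1 needs a stated exception. If the common dose is below 80 mg/kg, arms 3 and 4 do not receive 80 mg/kg at close-out. Sample size, outcomes and analysis are unchanged.

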2. BACKGROUND INFORMATION AND SCIENTIFIC RATIONALE

2.1. Background Information

The overall goals of the proposed trial are to address the significant gaps with respect to our understanding of best approaches to treatment of children 1-4 years of age with intestinal schistosomiasis. This age window coincides with the current “praziquantel treatment gap,” which highlights the fact that this age group remains excluded from preventive chemotherapy campaigns, which represent the primary approach to reducing infections in endemic regions globally.^{1,2}

[figure not shown]

Figure II. Conceptualization of Specific Aims

One of the main reasons for this persistent treatment gap is that praziquantel (PZQ) has not been extensively evaluated in children under the age of 4 globally, despite its recent US FDA approval down to one years of age. A key goal of the proposed trial would be to provide data in support of a change in the “labeling” or indications for PZQ to include young children. To achieve these goals, we propose a randomized, quasi-double blind, trial of PZQ at two baseline doses (40 and

80 mg/kg) with placebo or re-treatment provided at 6 months employing the baseline dose given (**Figure I**). Though we will utilize a placebo (dextrose) tablet that is matched for color and size as closely as possible, it is possible that study staff administering the drug will be able to distinguish the two based on appearance or odour as they will need to crush the tablets. Subjects may be able to notice the bitter taste of praziquantel as opposed to placebo, though subjects in this trial are very young and less likely to mark this. This will also allow us to evaluate optimal treatment intervals (6 versus current 12 months) for intestinal schistosomiasis. Finally, we will assess the impact of treatment on key indicators of morbidity that have been implicated in schistosomiasis, yet never studied among children under the age of four. Demonstrating efficacy with respect to morbidity will support the prioritization of treatment for this vulnerable age group and will significantly contribute to the impetus to provide treatment, even in resource constrained settings.

Schistosomiasis, caused by three main species of tissue-invasive parasitic trematodes, affects over 200 million individuals globally.³ A significant proportion of the global burden of disease due to schistosomiasis, includes key morbidities that disproportionately affect children.⁴ Specifically, the primary disabilities attributed to schistosomiasis including undernutrition, linear growth stunting, anemia, and cognitive impairment largely affect children who have limited, crucial windows to achieve these key growth and developmental milestones. Importantly, children aged 1-4 years are most vulnerable to these morbidities given this period coincides with peak velocities of somatic and brain growth, with the highest global prevalence of anemia, linear growth stunting, and undernutrition occurring in this age group worldwide.^{5,6} Despite this vulnerability and likely increased risk of morbidity due to schistosomiasis, few if any studies have evaluated the effect of treatment on these key indicators of early childhood well-being.

